5.1 Inclusion Criteria

Participants are eligible to be included in the study only if all the following criteria apply:

1. Patients with MS randomized in CLARITY/CLARITY-EXT clinical trial(s) who have received ≥ 1 course of IMP (Cladribine Tablets or placebo).

or

Patients with their FCDE randomized in ORACLE MS clinical trial who have received ≥ 1 course of IMP (Cladribine Tablets or placebo).

Informed Consent

2. Can give signed informed consent, as indicated in Appendix 2 (Study Governance), which includes compliance with the requirements and restrictions listed in the ICF and this protocol. Data will be collected from the medical records of deceased or lost to follow-up patients if consent is obtained by participant's proxy/caregiver/legal representative or if an ICF waiver is in place, if permitted by local regulation and approved by the relevant EC/IRB.

5.2 Exclusion Criteria

Participants are excluded from the study if any of the following criteria apply:

Medical Conditions

Any condition, including any uncontrolled disease state other than MS, that in the Investigator's opinion, constitutes an inappropriate risk or a contraindication for participation in the study or that could interfere with the study objectives, conduct, or evaluation. If a patient is experiencing a confirmed or suspected relapse at the time of screening, the Medical Monitor is to be consulted to agree on a stabilization period (estimated to be between 4 weeks and 3 months) before Study Visit 1.

For specific exclusion criteria for the MRI sub-study please see Section 6.5.4.2 (MRI Sub-Study).

5.3 Lifestyle Considerations

5.3.1 Meals and Dietary Restrictions

Not applicable. This study does not have any meal/dietary restrictions to specify.

5.3.2 Caffeine, Alcohol, Tobacco, and Cannabinoid-containing Products

Twenty-four hours prior to Study Visits 1 and Study Visit 2, when cognitive assessments or MRI procedures may be performed, participants will abstain from alcohol and cannabinoid-containing products.

5.3.3 Activity

Not applicable. This study does not have any restrictions on participant activity level to specify.

5.4 Screen Failures

Individuals who do not meet the criteria for participation in this study (screen failure) may not be rescreened. Patients with confirmed or suspected relapses can remain in the study, and Study Visit 1 will be postponed until the patient has stabilized.

6 Study Intervention(s)

Study intervention is any investigational intervention(s), marketed product(s), placebo, or medical device(s) intended to be administered to a study participant per the study protocol.

6.1 Study Intervention(s) Administration

This study does not involve administration of any IMP. Participants enrolled will have participated in CLARITY/CLARITY-EXT and ORACLE MS clinical trials, where they received Cladribine Tablets or placebo according to those study protocols.

6.1.1 Medical Device(s) Use

Not Applicable. No medical devices are provided for use in this study.

6.2 Study Intervention(s) Preparation, Handling, Storage, and Accountability

Not Applicable.

6.3 Measures to Minimize Bias: Study Intervention Assignment and Blinding

6.3.1 Study Intervention Assignment

Not Applicable.

6.3.2 Blinding

Not Applicable.

6.3.3 Emergency Unblinding

Not Applicable.

6.4 Study Intervention Compliance

Not Applicable.

6.5 Concomitant Therapy

Record in the case report form (CRF) all concomitant therapies (e.g., medicines or nondrug interventions) used from the time the participant signs the informed consent until completion of the study, including any changes. For prescription and over-the-counter medicines, vaccines, vitamins, and herbal supplements, record the name, reason for use, dates administered, and dosing information.

The use of concomitant medications and therapies is not controlled as part of this study. The first sequential disease modifying MS therapy that was taken following treatment with Cladribine Tablets, and the categorization of the second sequential treatment following Cladribine Tablets (categorized by platform injectable therapies, monoclonal antibody disease modifying treatments, oral disease modifying treatments, other, and unknown treatments) will be assessed through retrospective review of the patient's medical records and captured as part of the CRF.

Contact the Medical Monitor for any questions on concomitant or prior therapy.

6.5.1 Rescue Medicine

There are no restrictions or instructions for rescue medicines for participants in this study. Participants will receive medicines as part of their usual care by their treating physician.

6.5.2 Permitted Medicines

There are no restrictions or instructions for permitted medicines for participants in this study. Participants will receive medicines as part of their usual care under their treating physician.

6.5.3 Prohibited Medicines

There are no prohibited medicines in this study. Study participants will receive medicines as part of their usual care under their treating physician.

6.5.4 Other Interventions

6.5.4.1 Optional Blood Sampling for Pharmacogenetics Testing

Patients willing to consent to provide an optional blood sample and who are seen at a site with available capabilities to store and ship samples will have a blood draw taken at Study Visit 1 for pharmacogenetics testing.

6.5.4.2 MRI Sub-Study

The population to be included in the MRI sub-study will be based on the availability/consent of the patient to perform a new MRI, availability of the original machine and other technical site capabilities that will be defined following assessment of site feasibility to conduct the MRI sub-study.

For study participants at selected sites where MRI assessments will be conducted, the following exclusion criteria will apply to the MRI assessment only:¹

- a. Female study participants who are pregnant²
- b. Patients were administered Cladribine Tablets through prescription or as part of another study within 6 month period before enrolment in the MRI Sub-study (i.e. patients participating in a clinical trial or observational study within the 6 month period before enrolment in the MRI Sub-study, but do not receive Cladribine Tablets as part of these studies, are allowed to participate in the sub-study).

Patients willing to provide their consent to participate in the MRI sub-study and who do not meet any of the above exclusion criteria will have an MRI without gadolinium taken. Any MRI scan will be performed according to a standard protocol detailed in a separate MRI scan user's manual. A central neuroradiology center will perform the analysis of all MRI scans. As with other laboratory tests and clinical measures, strict adherence to the MRI scanning protocol and prompt handling of the scans is essential in obtaining a meaningful result. A urine pregnancy test will be conducted in female patients of childbearing potential participating in the MRI sub-study within a week prior to the MRI assessment. A serum pregnancy test is also acceptable if available as per SOC. Verbal reporting of pregnancy status by the female patient is not acceptable. For pregnant female patients the MRI visit may be rescheduled for a later date (within the timeframes specified in Section 4.1) following pregnancy outcome.

Prior to patient assessment, each study site will be asked to send a 'test' or 'dry-run' scan to assess image quality and shipment procedures, to evaluate the accessibility of the electronic data carrier, and to assess the ability to correctly reposition patients to get comparable brain images. Only upon final approval of this test scan, sites will be allowed to begin assessing patients. Once patients are enrolled, the quality of the scans will be assessed as soon as possible, as part of an ongoing quality control procedure. Investigators will be informed about the acceptance of scans and the need for scans to be repeated due to protocol deviations.

¹ If patient is not eligible for MRI, MRI will not be performed but clinical data for other objectives may be collected.

² Due to unknown risks regarding rare foetal and childhood adverse event outcomes following exposure to MRI during pregnancy (Ray, 2016), MRI procedures will not be performed for female patients who are pregnant, but may be scheduled for a later follow up date following pregnancy outcome.

6.6 Dose Selection and Modification

Not Applicable.

6.7 Study Intervention After the End of the Study

Throughout the duration of the study, participants will continue to receive their SOC treatment. Once participants have concluded their participation in this study, they will continue to be treated as part of their usual practice and care.

6.8 Special Precautions

Subject to the applicable local laws and regulations, patients who cannot participate or complete the SoA due to cognitive impairment or relapsing episode and are thus not able to give informed consent will be given the opportunity to participate by their proxy/caregiver/legal representative providing consent on their behalf.

Study visits for participants who are relapsing can be postponed until it is appropriate for them to complete study visit assessments. The decision to postpone the study visit will be made at the discretion of the physician based on the ability of the patient to attend the clinic and complete the assessments without causing discomfort or harm to the patient.

6.9 Management of Adverse Events of Interest

Adverse events of special interest (AESIs) for this study as defined in the SmPC should be considered as a medically significant AE and reported to the Sponsor using a Serious Adverse Event (SAE) Report Form with all related information.

Three main categories of AEs were defined as AESI:

- Severe (\geq Grade 3) lymphopenia: Lymphopenia is an expected event based on the mechanism of action of cladribine, an adenosine deaminase-resistant analog of deoxyadenosine, that after conversion to its active triphosphate form (2-Cd-ATP), decreases peripheral lymphocyte counts; grading should be performed according Common Terminology Criteria for Adverse Events where Grade 3 is defined as $< 500/\text{mm}^3$ - $200/\text{mm}^3$.
- Infections: Defects in cell-mediated immunity and immunosuppressive conditions may predispose patients to infectious diseases.
- Malignancies: Immunodeficiency could lead to an increased risk for the development of malignancies; however, this is generally seen where immunosuppression is profound and long-lasting. Malignancy cases have been reported in MS patients treated with other DMDs. In view of these considerations the potential risk of malignancy for Cladribine Tablets has been thoroughly evaluated.

7 Discontinuation of Study Intervention and Participant Discontinuation/Withdrawal

7.1 Discontinuation of Study Intervention

Not Applicable.

7.1.1 Temporary Discontinuation

Not Applicable.

7.1.2 Rechallenge

Not Applicable.

7.2 Participant Discontinuation/Withdrawal from the Study

- A participant may withdraw from the study at any time, at his/her own request (i.e., withdrawal of consent), and without giving a reason.
- Patients' proxy/caregiver/legal representative may withdraw consent at any time as well, without giving a reason.
- For the MRI sub-study, the participant may be withdrawn by the Investigator due to participation in another clinical study if the participant receives Cladribine Tablets in the other clinical study.
- The participant may be withdrawn at any time at the discretion of the Investigator for safety, behavioral, or administrative reasons.
- The SoA specifies the data to collect at each follow-up visit, and any additional evaluations that need to be completed. These assessments are not mandatory, and patients can remain in the study if certain assessments (e.g. PROs) are not completed.
- Participants can withdraw consent for the optional pharmacogenetic testing any time; this does not preclude them from continuing in the study and complete other assessments.

The patient will be informed that any data collected from the signature of the informed consent until the point of withdrawal will be maintained and included in the analysis (pending review and approval by ECs, IRBs and/or local regulations and patient consent). The Investigator should make every attempt to clarify the level of withdrawal: e.g., if the participant can still be contacted by phone for checking his/her status (e.g., alive or not). In case of withdrawal from the study, the appropriate CRF section must be completed.

If a participant withdraws consent from the optional pharmacogenetic testing before the samples have been analyzed, the participant's samples will be destroyed without being analyzed. In addition, data collected will be excluded from the analysis. If a participant withdraws from the pharmacogenetic testing after the participant's sample has been analyzed, any information learned from the analysis will remain part of the study database and may not be removed.

Participants or their proxy/caregiver/legal representative will be informed that they have the right to withdraw from the study at any time, without prejudice to their medical care, and that they are not obliged to state their reasons. Any withdrawal must be fully documented in the eCRF and source documents and should be followed up by the Investigator. The Investigator may withdraw a patient at any time if this is considered to be in the patient's best interest.

Participants who are discontinued/withdrawn from the study will not be replaced.

7.3 Lost to Follow-Up

A participant will be considered lost to follow-up if he or she repeatedly fails to return for scheduled visits and is unable to be contacted by the study site.

The following actions must be taken if a participant fails to return to the clinic for a required study visit:

- The site must attempt to contact the participant and reschedule the missed visit as soon as possible, counsel the participant on the importance of maintaining the assigned visit schedule and ascertain if the participant wants to or should continue in the study.
- Before a participant is deemed "lost to follow-up", the Investigator or designee must make every effort to regain contact with the participant: 1) where possible, make 3 telephone calls; 2) if necessary, send a certified letter (or an equivalent local method) to the participant's last known mailing address, and 3) if a participant has given the appropriate consent, contact the participant's general practitioner for information. These contact attempts should be documented in the participant's medical record.
- Should the participant continue to be unreachable, he/she will be considered to have withdrawn from the study.

8 Study Assessments and Procedures

- Study assessments and procedures and their timing are summarized in Section 1.3 (Schedule of Activities).
- **No** protocol waivers or exemptions are allowed.
- Immediate safety concerns should be discussed with the Sponsor immediately upon occurrence or awareness to determine if the participant should continue the study.
- Adherence to the study design requirements, including those specified in the SoA, is essential and required for study conduct.
- All screening evaluations must be completed and reviewed to confirm that potential participants meet all eligibility criteria. The Investigator will maintain a screening log to record details of all participants screened, to confirm eligibility, and if applicable, record reasons for screening failure.
- Prior to performing any study assessments that are not part of the participant's routine medical care or before entering data in the study electronic data capture (EDC) system, the Investigator will confirm that the participant or the participant's proxy/caregiver/legal representative has provided informed consent. Data will be collected from the medical records of deceased or lost to follow-up patients if consent

is obtained by participant's proxy/caregiver/legal representative or an ICF waiver is in place, if permitted by local regulation and approved by the relevant EC/IRB.

- Procedures conducted as part of the participant's routine medical care (e.g., pregnancy test for MRI sub-study) and obtained before signing of the ICF may be used for screening or baseline purposes provided the procedures met the protocol-specified criteria and were performed within the time frame defined in the SoA.

8.1 Efficacy Assessments and Procedures

A detailed schedule of study procedures/assessments is provided in the SoA (Section 1.3).

During the Screening Visit, the patient or their proxy/caregiver/legal representative will be informed of the study objectives and overall requirements, and informed consent will be obtained prior to any study specific assessments, unless an ICF waiver is in place (see Appendix 2 Study Governance for details on informed consent process). The site will also confirm that patients meet the Inclusion/Exclusion Criteria. During this visit, a complete Screening Evaluation will be performed, which will capture sociodemographic and clinical characteristics (including gender, age/year of birth, race and ethnicity where permitted, employment status and education level attained), medical history, and disease history (including classification of disease and diagnosis date). These screening activities may be administered by telephone if the patient is unable to attend the clinic for study visits, dependent on approval by ECs, IRBs, and/or local regulations. For patients participating only in retrospective data collection, local requirements for patient consent will be observed, which may include informed consent waiver.

PRO questionnaires, followed by cognition assessments (for ORACLE MS patients only), should be performed prior to any other assessments.

For patients participating in the MRI assessment, attempts should be made to perform Study Visit 2 within 3 months (maximum) after completing Study Visit 1 (maximum 4 weeks from Study Visit 1 after the last patient has been recruited). A urine pregnancy test will be performed within a week prior to the MRI assessment in female patients of childbearing potential. A serum pregnancy test is also acceptable if available as per SOC. Verbal reporting of pregnancy status by the patient is not acceptable. The Investigator will ensure that the patient or the patient's proxy/caregiver/legal representative has provided specific informed consent to participate in MRI assessments.

8.1.1 Clinical Endpoints

8.1.1.1 Expanded Disability Status Scale (EDSS)

The EDSS is a neurological assessment that will be used to assess the long-term disability progression following treatment with IMP in the parent studies (Appendix 5 Expanded Disability Status Scale (EDSS)). EDSS is a scale from 0-10 that evaluates a person with MS's disability/neurologic function level with 6 being the critical point at which a patient requires ambulatory assistance. The primary endpoint of proportion of study participants using a wheelchair (defined as unable to walk beyond approximately 5 meters even with aid,

essentially restricted to wheelchair; wheels self in standard wheelchair and transfers alone; up and about in wheelchair some 12 hours a day) the majority of the time in the 3 months prior to Study Visit 1 or participants are bedridden any time prior to Study Visit 1 determined via an EDSS score of 7.0 or higher (if available), or alternative clinical description data in medical records. The secondary endpoint will be determined as the proportion of study participants with EDSS of 6.0 or higher by EDSS documentation or alternative clinical description in medical records after last IMP from parent study.

Sustained disease progression is important because transient increases in the EDSS may also be due to relapses, which reflect disease activity rather than disease progression (Healy, 2013); an EDSS measurement taken at a single point in time may be subject to measurement error (Goodkin, 1992). As such, confirmation of sustained EDSS score is needed to mitigate against measurement error and EDSS fluctuation (Kalincik, 2015).

Furthermore, while EDSS scores at any timepoint, regardless of their relationship to relapses, may serve as evidence of EDSS progression, it is generally recommended that only EDSS scores that are recorded more than 30 days from the onset of a preceding relapse be used in order to confirm progression events (Kalincik, 2015). As such, Investigators in this study will be instructed to exclude any EDSS score recorded within 30 days of a previous relapse.

The in-person EDSS will be completed by the evaluating physician for those study participants who can come to the clinic for Study Visit 1. Alternatively, a telephone EDSS score can be determined by telephone interview in which trained clinical site staff member to administer the EDSS telephone questionnaire (Lechner-Scott, 2003). The telephone EDSS will be collected only from patients not attending clinic visits, and will be collected within 14 days of obtaining informed consent. Only one mode of the collection (in-person during a clinic visit, or by telephone) is required per patient. Retrospective EDSS scores will be ascertained from medical records for the time period between end of parent study to Study Visit 1 (when available).

Reasons for inability to come to the clinic for Study Visit 1 may include travel/migration, or limited mobility (bedridden), or clinical site restrictions due to COVID-19. In addition, patients may not want to come to the clinic for Study Visit 1 due to a lack of interest..

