1.3 Schedule of Activities

Table 1 Schedule of Activities: Assessments Captured at Each Study Visit provides details on the SoA.

Table 1 Schedule of Activities: Assessments Captured at Each Study Visit

	Screening	Study Visit 1	Study Visit 2	Notes
Assessments & Procedures		Within 2 weeks of Screening (in case of relapse: 4 weeks to 3 months)	Within 3 months^a of Study Visit 1	Screening assessments may be administered remotely if patient is unable to attend clinic for Study Visit, depending on approval by Ethics Committees (ECs), Institutional Review Boards (IRBs), and/or local regulations. Study Visit 1 time window does not apply if Screening and Study Visit 1 are combined.
Informed consent	X			If patient has passed away or is lost to follow-up, informed consent may be obtained from proxy/caregiver/legal representative, or an informed consent form (ICF) waiver may apply, depending on approval by ECs, IRBs, and/or local regulations.
Inclusion and exclusion criteria	X			
Sociodemographic and clinical characteristics	X			Includes parent study patient ID, gender, age/year of birth, race, ethnicity, employment status and education level attained, for sites where EC approval has been granted for collecting such data.
Prospective data collection				
Physical examination including vital signs		X		
Expanded Disability Status Scale (EDSS): In-person (clinic visit) or telephone (remote visit only) ^b		X		The in-person EDSS is evaluated during Study Visit 1. The telephone EDSS is administered within 14 days after appropriate informed consent has been obtained, and is only to be collected for patients not attending in-person at Study Visit 1. Only 1 mode of EDSS administration (either in-person or by telephone) is required.

	Screening	Study Visit 1	Study Visit 2	Notes
Assessments & Procedures		Within 2 weeks of Screening (in case of relapse: 4 weeks to 3 months)	Within 3 months^a of Study Visit 1	Screening assessments may be administered remotely if patient is unable to attend clinic for Study Visit, depending on approval by Ethics Committees (ECs), Institutional Review Boards (IRBs), and/or local regulations. Study Visit 1 time window does not apply if Screening and Study Visit 1 are combined.
EuroQoL-5 Dimensions (EQ-5D-3L)		X		
Brief Visuospatial Memory Test Revised (BVMT-R)		X		Administered only for ORACLE MS subjects only in countries where these instruments were used in CLASSIC MS study
Symbol Digit Modalities Test (SDMT)		X		

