The third potential clinic visit is Study Visit 2, which involves an MRI scan without gadolinium in approximately 150 patients who are willing to participate in this MRI sub-study. The sites that participate in the MRI sub-study will be selected primarily based on their technical capabilities to perform the required MRI assessments and the availability of the original MRI machine from the parent studies. The patients at these sites will be selected based on being able to fulfill the eligibility criteria (see Section 6.5.4.2), including the availability/consent of the patient to perform a new MRI and the provision of a urine pregnancy test within a week prior to the MRI assessment (for female patients of childbearing age). A serum pregnancy test is also acceptable if available as per standard of care (SOC). Verbal reporting of pregnancy status by the female patient is not acceptable. AEs and concomitant medications will also be reviewed and recorded during this visit. For patients who are not experiencing relapse at the time of screening, the duration between Screening Visit to Study Visit 1 is no more than 2 weeks, including for patients who are participating remotely and who are completing a telephone EDSS assessment only. For patients experiencing relapse, the duration between Screening and Study Visit 1 is between 4 weeks and 3 months. For patients selected to participate in the MRI sub-study, an additional visit will be required that will occur within a maximum of 3 months of Study Visit 1 (maximum 4 weeks from Study Visit 1 if last patient recruitment has occurred), and these patients' total study duration will likely be no more than 3.5 months if the patient was not experiencing relapse at Screening, or up to 6 months maximum in the case of relapse. For patients providing samples for pharmacogenetic testing, the time window for sample collection is up to a maximum of 6 months from Screening (unless last patient enrolled has occurred, in which case the testing must occur at Study Visit 1). Sites will be asked to enter any retrospective data into the electronic case report form (eCRF) for this study within 12 weeks of enrolling the patient. Participants who are eligible will be given the option of completing the screening, Study Visit 1, and 2 (where facilities for MRI are available) on the same day if prefer to do so and meet the eligibility criteria on that day (e.g. abstention from alcohol or cannabinoid products in the preceding 24 hours). Participants who are undergoing relapse or suspected relapse at the time of screening will be invited for Study Visit 1 after a stabilization period determined through consultation with the medical monitor.

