14.1 Primary Endpoint

The primary efficacy endpoint of this study will be evaluated descriptively by percentage and 95% CI of patients using a wheelchair most of the time ($EDSS \geq 7$) in the 3 months prior to Study Visit 1 or patients bedridden any time prior to visit 1. Forest plots will also be used to display these results.

In addition, analysis will be adjusted via logistic regression with parent studies (CLARITY or ORACLE), treatment group, and disease duration (at study visit 1) as continuous variable as factors for cohort A and with only disease duration (at study visit 1) as factors for cohort B, C and D. Estimate with likelihood based 95% CI within each parent study treatment group (exposed/not exposed) will be presented.

To identify the primary endpoint, the following source data used will be:

- Both AWB eCRF page and retro EDSS page will be considered. ($EDSS \geq 7$ in the 3 month prior to SV1 or $EDSS \geq 8$ after FDIMP)
- $EDSS \geq 7$ will also be considered (EDSS SV1).
- Participants who died due to MS are included in this proportion also (reason of death is MS disease related).

Disease duration = $(SV1 - \text{date of MS diagnosis} + 1) / 365.25$

Date of MS diagnosis is taken from CLARITY eCRF for CLARITY and CLARITY EXTENSION patients. For ORACLE MS patient, the MS diagnosis is the date of CDMS conversion collected either during the parent study or after the end of the parent study until SV1.

Logistic Regression:

The following SAS code will be used:

```
proc genmod data=sourcedata;
where avalc ne "U";
class STUDY TRT ;
model avalc = STUDY TRT DISEASE_DUR /dist=binomial link=logit lrci wald;
  Estimate "Never Exposed to Cladribine" intercept 1 Trt 1 0 / exp e;
  Estimate "Exposed to Cladribine" intercept 1 Trt 0 1 / exp e;
  Estimate "Never Exposed to Cladribine vs Exposed to Cladribine" Trt -1 1
/exp e;
  lsmeans trt / cl;
  ods output estimates=ESTIMATES lsmeans=lsmean; run;
```

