14.2 Secondary Endpoint

14.2.1 Long-term disability status

The secondary efficacy endpoint of this study will be evaluated descriptively by percentage and 95% CI of patients with EDSS of 6.0 or higher since last dose of IMP until Visit 1. The results of the confidence scale of EDSS values will be presented descriptively for worst EDSS score (available only for Retro EDSS). The worst EDSS value will be summarized by categories for each cohort.

EDSS will be assessed clinically (on site) and by phone.

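### The protocol's 30-day relapse exclusion for EDSS has no counterpart in the SAP and does not reach parent-trial scores, so a transient score can become a permanent EDSS 6 event

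*Protocol*

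**What the plan says.** **The rule.** Protocol 8.1.1.1 explains that EDSS can rise briefly because of a relapse and states that "confirmation of sustained EDSS score is needed to mitigate against measurement error and EDSS fluctuation". It cites a general recommendation that "only EDSS scores that are recorded more than 30 days from the onset of a preceding relapse be used" to confirm progression, and turns this into a site instruction: "Investigators in this study will be instructed to exclude any EDSS score recorded within 30 days of a previous relapse".

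**The windows.** Protocol 4.1 gives patients not in relapse at screening up to two weeks to Study Visit 1, remote participants included. It then says: "For patients experiencing relapse, the duration between Screening and Study Visit 1 is between 4 weeks and 3 months". For remote participants, Table 1 of the Protocol says: "The telephone EDSS is administered within 14 days after appropriate informed consent has been obtained". Neither that row nor 8.1.1.1 attaches a relapse condition to the telephone score.

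**The SAP.**
- 14.2.1 counts "patients with EDSS of 6.0 or higher since last dose of IMP until Visit 1".
- 14.3.2 takes the earliest of wheelchair use, ambulatory device use, an EDSS of 6 or more, or MS death as the event, timed from the first and from the last dose.
- 14.1 uses the ambulatory/bedridden page, the retrospective EDSS page and the Study Visit 1 EDSS.

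None of these sections mentions the 30-day rule or a confirmatory score. SAP section 7 declares no change from the protocol's analyses.

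**The concern.** An endpoint of the form 'ever reached EDSS 6' cannot be undone. A patient who scores 6.0 at one relapse visit and 2.5 at every later visit is an event in 14.2.1, and in 14.3.2 the event time is set at the relapse. This is the kind of score that the protocol says should not be used.

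The site instruction can work only on scores that CLASSIC sites handle. Where EDSS comes from the parent-trial databases, nobody is assigned to apply the rule. Scores on either side of the end of the parent study could then be treated differently within one endpoint, and the report would not show it. Even for scores that sites do handle, neither document describes a check of EDSS dates against relapse dates, so compliance could not be audited.

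**Working it through.** **1. Which scores can the site instruction reach?**

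| EDSS source | Entered by CLASSIC site? | Site exclusion can act? | SAP filter? |
|---|---|---|---|
| Retrospective page, end of parent study to Study Visit 1 (Protocol Table 1, 8.1.1.1) | Yes | Yes | None |
| Study Visit 1, in person or by telephone | Yes | Yes | None |
| Parent-trial datasets (SAP 6.3) | No | No | None |

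**2. Do the endpoint periods include parent-trial time?** Retrospective collection starts at the end of the parent study. The period in 14.2.1 starts at the last dose, and 14.3.2 starts at the first dose or the last dose. SAP 6.2 places ORACLE MS end-of-trial assessments after 24 weeks of follow-up from the last dose, and adds 24 weeks of safety follow-up after the 96-week CLARITY EXT period. So there is post-dose time that only parent data can cover. SAP 6.3 says that parent SDTM and ADaM data are used. That parent EDSS values feed 14.2.1 and 14.3.2 is an inference from these sections; neither section says so outright.

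**3. The primary endpoint.** The EDSS of 8 or more in 14.1 is labelled as after first dose, but the sources listed are CLASSIC eCRF pages and the Study Visit 1 score. On that reading, parent-trial EDSS does not enter.

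**4. The windows against 'more than 30 days from onset'.** Let d be the days from relapse onset to Screening, and s the days from Screening to Study Visit 1.
- In relapse at screening: s is at least 28, so d + s is 30 or less only if d is 0 to 2 and the visit falls at the very start of the window. The maximum gap is 30 − 28 = 2 days.
- Not in relapse at screening: s is 0 to 14, and 4.1 sets no minimum for d. A relapse that settled shortly before Screening can give d + s of 30 or less.
- Telephone: the 14-day limit lies wholly inside 30 days. Table 1 and 8.1.1.1 give no relapse condition, while 4.1 ties the two-week limit to patients not in relapse.

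**5. Scale.** The only sizing figure in the plan is the precision table in Protocol 9.2. At n = 587 and 5%, a Wald interval with finite-population correction gives 1.96 × √(0.05 × 0.95 / 587) × √(1 − 587/1958) = 1.475%, against the stated 1.48%. That equals 0.0148 × 587 = 8.7 patients. It serves only as a yardstick.

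*Study Visit 1 scores at risk.* P(onset in the 30 days before the visit) = 1 − exp(−ARR × 30/365.25). The ARRs 0.14 and 0.33 are the two-year CLARITY rates in Protocol 2.2; 0.05 is an assumed low case.

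| ARR | Probability | Of 587 |
|---|---|---|
| 0.05 | 0.41% | 2.4 |
| 0.14 | 1.14% | 6.7 |
| 0.33 | 2.67% | 15.7 |

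For each rate this is an upper bound: it assumes no relapse deferral, and only scores pushed across a threshold and not excluded by the site would become false events.

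*Ever EDSS 6 or more.* Assume about 10 years of follow-up and that a fraction q of relapses leaves an unexcluded transient score of 6 or more. False events = 1 − exp(−ARR × 10 × q).

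| ARR | q = 0.5% | q = 2% |
|---|---|---|
| 0.05 | 0.25% (1.5 of 587) | 1.0% (5.8) |
| 0.14 | 0.70% (4.1) | 2.76% (16.2) |
| 0.33 | 1.64% (9.6) | 6.39% (37.5) |

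No document gives q. The table shows how far the answer depends on it.

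**The case against.** Much can be said for the plan.

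- The instruction covers any EDSS score, which includes Study Visit 1 and telephone scores. A window that permits an assessment does not make the score usable. This stands.
- Protocol 6.8 lets study visits be postponed for any participant who is relapsing, not only at screening. Section 5.2 covers suspected relapse through the Medical Monitor. Section 4.1 applies the 4-week to 3-month window to patients in relapse without excluding remote ones, and asks only for attempts to meet the 14 days. Figure 2, which sets out the remote windows, is not visible in the text reviewed. A reader might infer that the schedule forces relapsing patients to be scored too early; the documents do not support that. What remains is inconsistent wording, and postponement under 6.8 that is discretionary with no 30-day floor.
- The 28 against 30 day difference compares clocks with different starts and is trivial.
- Section 8.1.1.1 also says that scores at any time may be evidence of progression. This blurs the rule, but the instruction to exclude follows directly.
- Relapse dates are recorded only if available (Protocol 8.1.1.7). SAP 9.5 imputes partial dates to the 15th of the month or 15 June, so a programmed filter will misclassify some scores. This stands and has to be handled in the fix.
- The study is exploratory and tests no hypothesis. That limits the consequence, but the proportions with 95% CIs are the results to be reported.

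**Conclusion.** The point holds for SAP 14.2.1 and 14.3.2: applied as written, they can count scores that the protocol excludes, while SAP section 7 declares no change. It rests on the inference that parent-trial EDSS supplies the time between dosing and the end of the parent study. For 14.1 the risk is limited to retrospective, Study Visit 1 or telephone scores that a site fails to exclude.

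The size cannot be derived from the documents; the figures above are illustrations under stated assumptions.

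Nor can the direction. A reader might take the CLARITY rates, 0.33/0.14 = 2.4, to mean that the never-exposed group gains 2.4 times as many false events. The documents do not support this. The ratio counts relapses, not scores of 6 or more. CLARITY placebo patients who entered CLARITY EXT were assigned cladribine (SAP 6.2) and are analysed as exposed (SAP 8.2.1). For the 867 of 1,326 CLARITY patients who entered the extension, the post-dose period starts in the extension; only 1,326 − 867 = 459 (35%) have their last dose in CLARITY. ORACLE MS patients are outside the ratio altogether.

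The EDSS worsening criterion in SAP 8.2.2 needs no change: a recorded new relapse already makes the patient a non-responder there.

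**What to change.** **SAP 14.1, 14.2.1 and 14.3.2.**
- Name every EDSS source, and say explicitly whether parent-trial scores are used.
- Flag and exclude by program any EDSS dated 0 to 30 days after a recorded relapse onset, in all sources: parent databases, retrospective page, and Study Visit 1 on site and by telephone.
- Keep all scores in the database, flagged rather than deleted.
- Report a sensitivity analysis without the filter.
- State how imputed relapse dates are treated. Under SAP 9.5 a missing day can be wrong by up to 31 − 15 = 16 days. A missing day and month can be wrong by up to 199 days (15 June to 31 December), far more than the 30-day window. One option is to mark such scores as undetermined and show results with and without them.

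**Protocol.** Reconcile the telephone wording in Table 1 and 8.1.1.1 (14 days, no relapse condition) and the Study Visit 1 window in 4.1 (counted from Screening, not from onset) with the 30-day rule.

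**Cost.** The programming is small and uses relapse onset dates already collected in CLASSIC (Protocol 8.1.1.7) and relapse dates already used from the parent trials (SAP 8.2.2). Some scores will be lost or misclassified where dates are partial or missing. The window wording needs a protocol amendment with IRB/IEC approval.
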